10.7.2 Medications leading to study product discontinuation

The following medications will result in study product discontinuation. As described in Section 10.6.3, the patient should however continue other study procedures until Week 36 for the primary analysis and as much as possible in the Extended Follow up if applicable.

- Pulse dose CS (≥ 250 mg prednisone equivalent/day)
- Potent immunosuppressive drugs such as cyclophosphamide, cyclosporine A, oral tacrolimus
- Biological disease modifying products, including belimumab, anti-IFN monoclonal antibodies
- Anti-B-Cell therapy, such as rituximab (RTX) and epratuzumab,
- Any investigational or non-registered product (drug or vaccine) other than the study product
- Any live vaccine (e.g., nasal influenza vaccine, oral poliomyelitis vaccine, measles-mumps-rubella vaccine, yellow fever vaccine, Japanese encephalitis vaccine, dengue vaccine, rotavirus vaccine, varicella vaccine, zoster vaccine, BCG, oral typhoid vaccine)

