13.6 Analysis Populations

Intention-to-treat analysis population

The efficacy analysis population is the intention-to-treat analysis population (ITT). It will include all randomized patients who received at least one dose of study product. This population will be analyzed according to the result of the random treatment assignment.

Per protocol population

The PP population will be a subset of the ITT including all randomized patients who met all inclusion and exclusion criteria, received at least one dose of study product, did not meet any elimination criteria during the study, and complied with the procedures defined in the protocol (*i.e.*, who did not have major protocol deviations that could impact the primary endpoint analysis). This will be the population used in the immunogenicity analysis.

Safety population

The safety population (SP) will include all patients who received at least one dose of study product (placebo or IFN-K). The patients in the SP are analyzed according to the treatment actually received. This will be the population used in the safety analysis.

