3.1.1 Major protocol deviations

Major protocol deviations leading to patient's exclusion from the Per Protocol population are defined as deviations liable to prevent or change the interpretation of the results of the primary efficacy analysis of the study. The following deviations may be considered as major (the list is not exhaustive and maybe modified at the time of the blind review):

- Non-compliance with the inclusion or non-inclusion criteria
- non-compliance with the randomization procedure
- non-compliance with study treatment
- intake of forbidden medication

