3.3.2 Per-protocol (PP) dataset

The PP population will be a subset of the FAS including all randomized patients having received at least one dose of study product (IFN-K or placebo), and who complied with the procedures defined in the protocol (*i.e.*, who did not have major protocol deviations that could impact the primary endpoint analysis).

In addition, patients with at least one of the following cases will be excluded from the PP population:

- missing IFN gene signature at baseline
- missing IFN gene signature at week 24 and week 36
- missing BICLA at week 36, *i.e.*:
 - all missing BILAG at baseline
 - or missing BILAG at week 36 corresponding to a BILAG A or B at baseline
 - or all missing BILAG at week 36

Statistical Analysis Plan

Study Name: IFN-K-002

SAP version & date: v4, 18/Jun/2018

- or missing SLEDAI-2K at baseline
- or missing SLEDAI-2K at week 36
- or missing PGA on VAS 100 mm at baseline
- or missing PGA on VAS 100 mm at week 36
- less than 4 doses of study product received (out of 5)

This will also be the population used for the immunogenicity, autoantibodies and biomarkers analyses.

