Total scores at each visit and change from baseline by treatment group will be presented. The change at Week 36 will be analyzed using a t-test. (Statistical tables 14.2.39.1 to 14.2.39.2)

All FACIT data will be presented in Listing 16.2.6.14.

5.2.4.5.7 **Autoantibodies**

The levels of auto-antibodies (ANA, anti-dsDNA, anti-Smith antigen [anti-Sm], anti-RNP, anti-SSA/Ro, anti-SSB/La, anti-cardiolipin, and anti- β 2-glycoprotein I antibodies) will be described at each visit by treatment group. Change from baseline by treatment group will be presented for quantitative parameters. For anti-dsDNA, the change at Week 36 will be analyzed using a t-test. (Statistical tables 14.2.40.1 to 14.2.40.2). These analyses will be performed on the PP population.

All auto-antibodies data will be listed in Listing 16.2.6.15.

5.2.4.5.8 **Biomarkers**

The biomarkers (C3, C4, CH50) at each visit and change from baseline by treatment group will be presented. (Statistical tables 14.2.41.1 to 14.2.41.2). For C3 the change at Week 36 will be analyzed using a t-test. These analyses will be performed on the PP population.

All biomarkers data will be listed in Listing 16.2.6.16.

5.2.4.5.9 **Anti-IFN α and anti-KLH antibody isotyping**

Descriptive analysis will be performed on Anti-IFN α and anti-KLH antibody isotyping data. (Statistical table 14.2.42)

All corresponding data will be listed in Listing 16.2.6.17.

5.2.4.5.10 **Anti-Hemagglutinin antibody response following influenza vaccination**

Seroconversion (four folds increase in antibody titers post-vaccination) and seroprotection (HIA antibody titers \geq 1:40 post-vaccination) will be presented by treatment group for each visit. In addition, results by visit will be presented according to status of anti-IFN α neutralizing antibodies (positive/negative) at the corresponding visit (Statistical table 14.2.43). These analyses will be performed on the FAS population, only on patients vaccinated with seasonal Flu and with sample at baseline and post-baseline.

Statistical Analysis Plan

Study Name: IFN-K-002

SAP version & date: v4, 18/Jun/2018

All corresponding data will be listed in Listing 16.2.6.18.

5.2.4.5.11 ***Neutralizing Anti-IFN α antibodies towards IFN α subtypes***

Descriptive analysis will be performed on Neutralizing Anti-IFN α antibodies towards IFN α subtypes data. (Statistical table 14.2.44)

All corresponding data will be listed in Listing 16.2.6.19.

5.2.4.5.12 ***Other***

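### The only Week 36 between-arm tests of C3 and anti-dsDNA run on a per-protocol set selected on events after randomisation; the FAS should be the main population, with per-protocol as support

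*SAP*

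**What the plan says.** **The PP set (SAP 3.3.2).** Beyond major deviations, a patient is excluded for any of the following:
- no baseline gene signature, or "missing IFN gene signature at week 24 and week 36" (both must be absent);
- "missing BICLA at week 36", meaning that SLEDAI-2K or PGA is missing at baseline or Week 36, that all BILAG is missing at either time, or that a Week 36 BILAG grade is missing for a system graded A or B at baseline;
- fewer than four of the five doses.

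SAP 3.1.1 gives an open list of possible major deviations, which includes "intake of forbidden medication". They are adjudicated at a blinded review (SAP 3.1).

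**Where PP is used.** SAP 3.3.2 adds: "This will also be the population used for the immunogenicity, autoantibodies and biomarkers analyses". The default for exploratory analyses in SAP 5.2.4.5 is the FAS, but 5.2.4.5.7 puts the anti-dsDNA t-test on PP, and 5.2.4.5.8 reads "For C3 the change at Week 36 will be analyzed using a t-test. These analyses will be performed on the PP population". The table list (SAP 10.1) shows Tables 14.2.40.1 to 14.2.41.2 under PP, with no FAS counterpart.

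**The protocol.** Section 13.6 makes ITT (the SAP's FAS) the efficacy population and says of PP: "This will be the population used in the immunogenicity analysis". Section 13.9.4 repeats this for immunogenicity. Section 13.9.6 names no population for autoantibodies or biomarkers. SAP 7.1 records only the relabelling of ITT as FAS, and nothing else in Section 7 covers the wider use of PP.

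**Follow-up after stopping product.** Protocol 10.7.2 says "The following medications will result in study product discontinuation". That section and 10.6.3 both ask such patients to continue study procedures to Week 36.

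**The concern.** Randomisation makes the two arms comparable as allocated. Doses received, attendance for the Week 36 disease scores and deviations during the trial all come later and can depend on treatment, through flare, added lupus medication or adverse reactions. Comparing C3 and anti-dsDNA only among patients who pass these filters compares selected groups.

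The direction cannot be assumed. If more IFN-K patients with poor outcomes are removed, the result favours IFN-K. If more placebo patients are removed after needing excluded medication, it works against IFN-K.

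What is at stake is the trial's supporting biological evidence: whether IFN-K shifts two recognised disease markers. The success criterion is not affected.

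**Working it through.** **1. Do the exclusions bear on the samples?** Dose count, Week 36 SLEDAI-2K, PGA and BILAG, and deviations during treatment are settled after randomisation. A patient can fail any of them and still have a valid baseline and Week 36 C3 and anti-dsDNA. Blinded adjudication of deviations keeps the reviewers from favouring an arm. It does not stop the underlying events from differing by arm.

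**2. Which patients differ between FAS and PP at Week 36?** C3, anti-dsDNA, BILAG, SLEDAI-2K and PGA are all collected at Visit 12 (Protocol 10.9.12), and SAP 5.3.2 imputes no missing laboratory value. A patient who leaves before Week 36 therefore normally has no Week 36 value in either population. The group at issue has a Week 36 sample but fails a PP rule. For the dose rule, with doses at Weeks 0, 1, 4, 12 and 24:
- stopping before Week 12 leaves at most 3 doses, so the patient is excluded;
- missing only Week 24 leaves 4 doses, so the patient is retained unless a major deviation applies.

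**3. Size.** The plan gives no figure to reproduce: no PP exclusion rate, and no SD or power for C3 or anti-dsDNA. Let d be the share of an arm's patients with a value whom PP drops, and g the gap in SD between retained and dropped patients. The whole-arm mean is M = (1 − d)R + dE, with R the retained and E the excluded mean, so R − M = d(R − E) = d·g. Hence

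bias of the PP difference = d_T·g_T − d_C·g_C (T = IFN-K, C = placebo).

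The type I error takes no true effect and a two-sided 5% t-test. It uses noncentrality = bias / √(1/n_T + 1/n_C) and n = 89(1 − d), with 89 per arm from the protocol's enrolment and every patient assumed to have a Week 36 value. All d and g below are assumptions.

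| d_T / d_C | g_T / g_C (SD) | Bias (SD) | Type I error |
|---|---|---|---|
| 10% / 10% | 0.5 / 0.5 | 0.05 − 0.05 = 0 | 5.0% |
| 10% / 10% | 0.5 / 0 | 0.05 − 0 = 0.05 | 6.1% |
| 15% / 5% | 0.5 / 0.5 | 0.075 − 0.025 = 0.05 | 6.1% |
| 10% / 10% | 1 / 0 | 0.10 − 0 = 0.10 | 9.6% |
| 20% / 10% | 1 / 1 | 0.20 − 0.10 = 0.10 | 9.4% |
| 30% / 10% | 1 / 1 | 0.30 − 0.10 = 0.20 | 21.7% |

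The top of this range is a choice of inputs, not a bound: 30% / 10% with a 1 SD gap in the IFN-K arm alone would give 0.30 SD and 42.2%.

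**4. Antibody titres.** SAP 5.2.4.4 reports seropositivity over time, log titres, reverse cumulative curves and GMTs with confidence intervals, and names no between-arm test. The issue there is whom the rates describe. Binding antibodies are sampled from Week 4 (Protocol 10.9.4), so a patient who leaves at Week 30 also disappears from the earlier visits. Dose count is tied to response: in the phase I-II study everyone given a fourth dose at 120 or 240 µg developed neutralising antibodies (Protocol 5.5), against 3/6 + 4/5 = 7 of 11 in those groups overall (Protocol 5.4.3). That fourth dose was conditional and planned for half the patients, so a smaller contrast should be expected here.

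**The case against.** **The endpoints are exploratory.** C3 and anti-dsDNA do not enter the success criterion, both co-primary endpoints are analysed on the FAS, and all autoantibody and biomarker data are listed. This stands and limits the severity.

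**The protocol named no population for these markers, and the SAP states PP openly.** This is correct, so the omission from Section 7 is a documentation gap. It does not answer the selection problem.

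**Bias is possible, not shown.** Also correct. Withdrawal reasons include withdrawn consent, pregnancy and loss to follow-up, and one listed trigger for stopping product is a live vaccine. With like exclusions in both arms the bias is zero.

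**The FAS does not cure missing data.** A Week 36 FAS t-test is still observed-case. This stands and shapes the fix.

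Three stronger readings are tempting, and the documents do not support them:
- *That every antibody analysis is on PP.* The text puts the anti-hemagglutinin response on the FAS (SAP 5.2.4.5.10). Efficacy and flare models by neutralizing status use the FAS (5.2.4.2, 5.2.4.5.2), and adverse events by that status use the safety set.
- *That no all-treated antibody result exists.* SAP 5.2.5.1 summarises presence of neutralizing antibodies on the safety set (Table 14.3.1). PP for immunogenicity was also prespecified in the protocol, and response after most of the intended course is a fair question.
- *That PP costs the planned 10% drop-out, 178 − 160 = 18 patients.* Most of those would have no Week 36 sample under the FAS either.

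**Conclusion.** The point holds for the post-baseline autoantibody and biomarker analyses. The Week 36 t-tests of C3 and anti-dsDNA are planned only on a set defined largely by post-randomisation events, with no FAS version. This departs from the SAP's own exploratory default and goes beyond the role the protocol gives PP. Patients with usable Week 36 samples are set aside for reasons unconnected with those samples.

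The bias is 0 to about 0.2 SD across the tabulated scenarios, which rest wholly on assumed exclusion shares and gaps. It requires the share, the gap or both to differ between arms; its actual size and direction cannot be known from the documents. For the anti-IFNα and anti-KLH tables the weakness is narrower: descriptive rates that apply to PP patients only. Overall severity is minor to moderate.

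**What to change.** 1. In SAP 3.3.2, 5.2.4.5.7 and 5.2.4.5.8, make the FAS the main population for post-baseline autoantibodies and biomarkers, and keep PP as support.
2. For the C3 and anti-dsDNA comparisons, use all available post-baseline values, for example in a repeated-measures model reporting the Week 36 difference. Protocol 10.9 schedules C3 at Weeks 4, 8, 12, 16, 24, 28 and 36, and anti-dsDNA at Weeks 12, 24 and 36. The SAP already plans such a model for the gene signature (5.2.4.2). State the missing-data assumption.
3. Keep the prespecified PP tables for anti-IFNα binding, neutralizing and anti-KLH titres. Add an all-treated version of the rates over time and GMTs, cross-referring to Table 14.3.1 for neutralizing-antibody presence.
4. Record the populations in SAP Section 7. Reconcile text and table list for Tables 14.2.42 to 14.2.44: the anti-hemagglutinin text says FAS, and the isotyping and IFNα-subtype texts fall under the FAS default, while the list appears to mark all three PP (column positions were read from extracted text).

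The cost is SAP wording, reruns of existing table programs, one added model for each of the two markers and some extra tables. Including under-dosed patients may dilute the observed effect; the supportive PP tables show the result in patients who received most of the course.

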3.3.3 Safety (SAF) dataset

The safety population (SAF) will include all patients who received at least one dose of study product (placebo or IFN-K). The patients in the SAF are analyzed according to the treatment actually received. This will be the population used for the safety analysis.

4 Endpoints for analysis

4.1 Efficacy endpoints

4.1.1 Primary efficacy endpoint(s)

Two co-primary endpoints are evaluated in the trial:

- Change from baseline in the expression of IFN-induced genes at Week 36.
- Response to treatment with IFN-K as measured by the British Isles Lupus Assessment Group (BILAG)-based Composite Lupus Assessment (BICLA) response criteria at Week 36:
 - All BILAG A scores at baseline improve to B/C/D and all BILAG B scores improve to C/D at Week 36
and
○ No BILAG worsening in other body systems: no new BILAG A or ≥ 2 new BILAG B scores at Week 36
and
○ No worsening in SLEDAI-2K total score at Week 36 compared with baseline
and
○ No deterioration in PGA (< 10% worsening) on VAS 100 mm at Week 36 compared with baseline
and
○ No addition or increased dose level of anti-malarial drugs or immunosuppressive drugs or corticosteroids between Week 24 and Week 36 (this criterion will be identified by medical review)

Statistical Analysis Plan

Study Name: IFN-K-002

SAP version & date: v4, 18/Jun/2018

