3.3 Analysis dataset definitions

3.3.1 Full Analysis Set (FAS)

The primary efficacy analysis population is the Full Analysis Set (FAS). It will include all randomized patients who received at least one dose of the study product (IFN-K or placebo). This population will be analyzed according to the result of the random treatment assignment.

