The study will be considered as positive if a statistically significant better effect of IFN-K compared to placebo is observed on the neutralization of the IFN gene signature (i.e. the first co-primary endpoint) and if at least a trend favoring IFN-K is observed on the BICLA response (i.e. the second co-primary endpoint). An observed 10% difference will be considered a marginal effect and a 15% difference will be considered as an important effect, whatever the statistical significance observed.

The primary efficacy analysis will be performed on the FAS set.

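### The BICLA co-primary looks at medication only from Week 24 to Week 36, so a patient given a product-stopping lupus drug earlier stays in the FAS and can be scored a responder

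*SAP*

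**What the plan says.** BICLA has five criteria, identical in protocol 13.2 and SAP 4.1.1. Four are judged on Week 36 BILAG, SLEDAI-2K and PGA against baseline. The fifth is the medication criterion: "No addition or increased dose level of anti-malarial drugs or immunosuppressive drugs or corticosteroids between Week 24 and Week 36". The SAP adds that "this criterion will be identified by medical review" and gives that review no wider remit.

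Protocol 10.7.2 opens with "The following medications will result in study product discontinuation". Its list includes pulse corticosteroid, "Potent immunosuppressive drugs such as cyclophosphamide, cyclosporine A, oral tacrolimus", biological products including belimumab and anti-IFN antibodies, and "Anti-B-Cell therapy, such as rituximab (RTX) and epratuzumab". The consequence is for dosing only: "the patient should however continue other study procedures until Week 36 for the primary analysis".

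On the analysis set, SAP 3.3.1 takes every randomized patient with one dose or more, analysed as assigned, and SAP 5.2.4.1 states: "The primary efficacy analysis will be performed on the FAS set". SAP 5.3.2 (missing data) attaches no BICLA consequence to rescue or to stopping product.

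The PP set (SAP 3.3.2) excludes patients with fewer than four of the five doses. It also excludes major deviations, for which SAP 3.1.1 names forbidden medication as something that may qualify.

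**The concern.** The endpoint is described as response to treatment with IFN-K. The definition already treats added lupus medication as failure, but only in the last 12 of 36 weeks. Drugs active enough in lupus to stop study product have no effect on the score if they start before Week 24. Continuing such a drug unchanged after Week 24 is neither an addition nor an increase.

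There is a second gap inside the window. Protocol 10.7.2 lists biologics and anti-B-cell therapy separately from immunosuppressive drugs, and the BICLA criterion names only antimalarials, immunosuppressive drugs and corticosteroids. Whether a biologic started at, say, Week 26 counts is left to the medical reviewers.

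At stake is who is called a responder on a co-primary endpoint. The observed BICLA difference also carries weight by itself: SAP 5.2.4.1 calls 10 points marginal and 15 points important, regardless of significance.

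**Working it through.** **Following one patient through the rules.** Doses fall at Weeks 0, 1, 4, 12 and 24 (protocol 9.1.3). Suppose a patient takes the first four, flares at Week 14, receives rituximab or cyclophosphamide, and is quiet at Week 36.

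- Product stops and the Week 24 dose is withheld; follow-up continues (10.7.2).
- FAS: included (SAP 3.3.1).
- BICLA: the four disease criteria are met. Nothing is added or increased from Week 24, so the fifth is met too. Score: responder.
- PP: four doses were received, so the dose-count exclusion does not apply. Removal depends on the deviation being judged major.

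Had the same patient stopped at Week 10, at most three doses would have been given and PP would exclude the patient automatically. The FAS result would be the same in both cases.

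**Other outputs.** Treatment failure (SAP 5.2.4.5.4) is exploratory, concerns corticosteroids only and starts at Week 24. The analysis of changes in lupus therapy was dropped as redundant with BICLA and LLDAS (SAP 7.2.2). For Weeks 0-24 it is not redundant, because BICLA does not look there and LLDAS is assessed at Week 36. SRI-4 (SAP 4.1.2.1) has no medication criterion, although SAP 5.2.4.3.1 says it could become the primary endpoint for further development.

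**The plan's own figure.** Inputs (protocol 13.1): p1 = 0.206, p2 = 0.406, n = 80 per arm, two-sided 5%. Continuity-corrected normal approximation, with mean rate 0.306:

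z = (|p2 − p1| − 1/n − 1.96·√(2·0.306·0.694/n)) / √((p1(1−p1) + p2(1−p2))/n)
= (0.2000 − 0.0125 − 0.1428) / 0.0711 = 0.63, so power is 73.5%.

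The stated 73% is reproduced (Fisher's exact test gives 74.1%).

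**Illustration of the scoring rule.** The documents give no rescue rate, so r and q below are assumptions. Let r be the share of an arm rescued before Week 24 and q the share of those who meet every other criterion at Week 36. Take 20.6% and 40.6% as the rates with rescue scored as non-response, which the documents do not state. As written, each arm's rate becomes p + r·q, so the difference moves by (r on IFN-K − r on placebo)·q.

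| Rescue placebo / IFN-K | q | Placebo | IFN-K | Difference |
|---|---|---|---|---|
| 10% / 5% | 0.2 | 22.6% | 41.6% | 19 points |
| 10% / 5% | 0.6 | 26.6% | 43.6% | 17 points |
| 5% / 5% | 0.2 | 21.6% | 41.6% | 20 points |
| 5% / 5% | 0.6 | 23.6% | 43.6% | 20 points |
| 5% / 10% | 0.2 | 21.6% | 42.6% | 21 points |
| 5% / 10% | 0.6 | 23.6% | 46.6% | 23 points |

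All six differences stay above the 15-point benchmark. A shift of up to 3 points either way matters only when the difference lies within 3 points of 10 or 15. For example, 16 points would be read as 16 − (0.10 − 0.05)·0.6·100 = 13.

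**The case against.** Following patients after they stop product and analysing them as randomized is a coherent treatment-policy approach, and one could say that the plan simply chose it. Part of this stands: retaining these patients in the FAS is right, and scoring rescue as non-response is one option among several. But neither document states such a strategy, and a definition that fails patients for medication added after Week 24 is not a treatment-policy endpoint. The 12-week look-back is unexplained.

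The PP repeat gives some protection, and not all of it is discretionary. Anyone who stops before the Week 12 dose is excluded by the dose count, and SAP 5.3.6 promises that substantial differences from the FAS will be explored. That stands. It does not cover rescue after the fourth dose, and PP is supplementary.

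A reader might infer that rescue will be commoner on placebo, that the effect is therefore biased towards zero, and that BICLA power falls well below 73%. The documents do not support this, for three reasons:

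- They contain no rescue rate for either arm, and rescue commoner on IFN-K would inflate the difference instead.
- They define BICLA in one way only. If 20.6% and 40.6% are rates under that definition, the 73% already refers to it and nothing falls.
- Significance on BICLA is not the success rule. SAP 5.2.4.1 asks for a significant gene-signature result plus a favourable trend on BICLA.

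**Conclusion.** The gap is real and should be closed before unblinding. As written, a patient given a 10.7.2 lupus drug before Week 24 remains in the primary analysis and is a BICLA responder if the other criteria are met; whether biologics count even after Week 24 is unclear. This follows from the text and needs no assumption.

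The effect on the result is not established in size or direction. Under the assumed 5-10% rescue per arm and 20-60% of rescued patients meeting the other criteria, the planned 20-point difference would be observed as 17 to 23 points, and would stay at 20 if rescue were equal. Those figures rest on reading the planning rates as rescue-counted-as-failure rates. They show that the rule can mislead either way, not that it will weaken this trial.

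**What to change.** State in SAP 4.1.1 and 5.2.4.1, with an entry in SAP section 7, that receipt of any lupus-active class listed in protocol 10.7.2 (pulse corticosteroid, potent immunosuppressant, biologic or anti-IFN antibody, anti-B-cell therapy) at any time from first dose to Week 36 is BICLA non-response. Apply the same rule to SRI-4. Keep the present definition as an FAS sensitivity analysis.

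Specify that the medical review is done blind, which SAP 4.1.1 does not say. It should use the on-study concomitant medication data (Table 14.3.24, Listing 16.2.4.9), which protocol 11.4.4 has recorded at each visit. The prohibited-medication table and listing (14.1.26, 16.2.4.8) sit in the SAP section on medical history and previous medications, so they may not show on-study use.

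One conflict must be reconciled first. Protocol Table 4 permits one short corticosteroid episode above 20 mg/day during induction and gives no upper limit, while 10.7.2 makes a pulse dose a reason to stop product. Reviewers need to know how to classify such an episode; no clinical rule is proposed here.

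The cost is modest: slightly lower response rates, and a documented change to the protocol's BICLA definition that has to be made before unblinding. No new data are needed.
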